### 8.5 STATISTICAL ANALYSIS

The main study database will be cleaned and locked for analysis after the last patient completes 12 months treatment.

The assessment of safety during the LT-OLE will be based on descriptive statistics and summarized by patient's treatment in the treatment period, and overall. No hypothesis testing will be performed. The descriptive statistics will include means, standard deviations, quartiles/ranges for continuous variables, and counts with percentages for categorical data. 95% CI will be used to further describe the clinical/auxological and biochemical endpoints.

The Sponsor reserves the right to stop enrollment when the targeted number of randomized patients is reached. If this situation arises, non-randomized patients that are undergoing Screening will be considered a Screen Failure.

Details of applicable statistical methods for the main study and LT-OLE will be provided in two separate SAPs prior to database lock of the main study and final study closure of the LT-OLE.

### 8.6 EFFICACY ANALYSIS

The aim of the present study is to demonstrate that in terms of the primary efficacy endpoint, Annualized HV at 12 months, weekly MOD-4023 is non-inferior to daily Genotropin® by a non-inferiority margin of 1.8 cm/year.

With  $\mu_M$  and  $\mu_C$  representing the mean annual HV for the MOD-4023 and the Genotropin® (Control) group, respectively, the following hypotheses will be tested:

Null hypothesis  $H_0$ :  $\mu_M < \mu_C - 1.8$  cm/year;

vs.

Alternate hypothesis  $H_1$ :  $\mu_M \geq \mu_C - 1.8$  cm/year

Non-inferiority will be concluded if the lower bound of the 2-sided 95 % CI for the mean treatment difference "MOD-4023 – Genotropin®", in the primary efficacy endpoint is  $\geq -1.8$  cm/year.

The CI for the difference of means between the 2 treatments will be derived from an analysis using ANCOVA. The ANCOVA model will include classification terms for treatment, age group, gender, peak hGH levels, and region. The model will also include Baseline Ht SDS as a covariate. The determination of non-inferiority will be based on least squares means for the 2 treatments from the ANOCVA and the 95 % CI of the differences between the treatments.

Descriptive statistics will be reported for observed and change from Baseline to annual HV values at 12 months during the main study and every 12 months thereafter.

ANCOVA-based statistics will be reported by the categorical terms used in the ANCOVA model: age group, gender, peak GH levels, and region.

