
SAMPLE SIZE CALCULATION
	
The aim of the study is to demonstrate that SC weekly MOD-4023 is non-inferior to SC daily Genotropin® administration with respect to the primary efficacy endpoint of annual HV in cm/year after 12 months of treatment.
 
Non-inferiority will be concluded if the lower bound of the 2-sided 95% confidence interval (CI) for the mean treatment difference (MOD-4023 – Genotropin®) in the primary efficacy endpoint is <math>>-1.8</math> cm/year.

Effective Date: Date of final electronic approval

	
The following assumptions were made in the sample size calculation:
 
 
• 2-sided alpha of 0.05,
 
• 80% power,
 
• between-patient standard deviation of annual growth rate of 2.5 cm/year in all treatment groups,
 
• non-inferiority margin of –1.8 cm/year,
 
• true mean treatment difference (MOD-4023 – Genotropin®) in the primary efficacy endpoint of –0.8 cm/year.
 
 
With these assumptions, 100 treated patients per group will provide 80% power for the non-inferiority test. To allow for an approximate 10% dropout rate, 110 patients will be randomized to each treatment group, for a total of 220 patients.

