
STATISTICAL ANALYSIS:
	
Details on the statistical methods will be provided in a Statistical Analysis Plan (SAP) prior to database lock.
 
The aim of the present study is to demonstrate that in terms of annual HV at 12 months (primary efficacy endpoint), weekly MOD-4023 is non-inferior to daily Genotropin® administration by a non-inferiority margin of 1.8 cm/year.
 
With <math>\mu_M</math> and <math>\mu_C</math> representing the mean annual HV at 12 months for the MOD-4023 and the Genotropin® (Control) group, respectively, the following hypotheses will be tested:
 
Null hypothesis <math>H_0</math>: <math>\mu_M < \mu_C - 1.8</math> cm/year;
 
Versus (vs.)
 
Alternate hypothesis <math>H_1</math>: <math>\mu_M \geq \mu_C - 1.8</math> cm/year
 
Non-inferiority will be concluded for the primary efficacy endpoint if the lower bound of the 2-sided 95% CI for the mean treatment difference (MOD-4023 – Genotropin®) is <math>\geq -1.8</math> cm/year.
 
Primary Efficacy Analysis: The CI for the difference of means between the 2 treatments will be derived from an analysis using Analysis of Covariance (ANCOVA). The ANCOVA model will include the stratification classes for treatment, age group, peak hGH value during stimulation test, region and gender, and Baseline Ht SDS as a covariate. The determination of non-inferiority will be based on least squares means for the 2 treatments from the ANCOVA and the 95% CI of the differences between the treatments.
 
Summary statistics for HV at end of treatment and for absolute change in HV from Baseline to end of treatment, will be presented by treatment group (and further stratified by factors used in the ANCOVA model).
 
Secondary Analyses: Annualized HV after 6 months of treatment, and change (from Baseline) in Ht SDS at 6 and 12 months will be summarized with descriptive statistics. These 3 endpoints will each be analyzed using a similar ANCOVA model as used for the primary endpoint, with terms for treatment and the randomization strata (age, peak hGH value during stimulation test, region), gender and baseline value for each endpoint of interest. The model-derived least square means and standard error (SE) will be used to construct 95% CI for the difference between treatment groups. These analyses are considered as supportive efficacy analyses.
 
Change in BM, calculated as BA/CA at the end of 12 months, compared to

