## 8. STATISTICAL ANALYSIS METHOD

### 8.1 SAMPLE SIZE CONSIDERATION

The aim of the main study is to demonstrate that weekly MOD-4023 is not inferior to daily r-hGH administration. Non-inferiority will be claimed if the 2-sided 95% CI for mean treatment difference (MOD-4023 – Genotropin®) in the primary efficacy endpoint will lie entirely above “non-inferiority margin” of -1.8 cm/year.

The following assumptions were made in the sample size calculation:

- 2-sided alpha of 0.05.
- 80 % power.
- Between-patient SD of annual growth rate is 2.5 cm/year in all treatment groups.
- Non-inferiority margin is -1.8 cm/year.
- The true mean treatment difference (MOD-4023 – Genotropin®) is -0.8 cm/year.

With these assumptions, 100 patients per group will provide 80 % power for the non-inferiority test. To allow for an approximate 10 % dropout rate, 110 patients will be randomized to each treatment group (Total N=220 patients).

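### The primary ANCOVA fits age in two classes and peak GH in three although exact values are on record, so it gives up a small amount of precision; adding exact age would cost one degree of freedom

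*Protocol*

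**What the plan says.** Protocol section 8.6 gives the primary model for 12-month height velocity: "The ANCOVA model will include classification terms for treatment, age group, gender, peak hGH levels, and region". Baseline height SDS is added as the one continuous covariate. The synopsis (Statistical Analysis) agrees: "The ANCOVA model will include the stratification classes for treatment, age group, peak hGH value during stimulation test, region and gender". Section 8.6 later refers to age group, gender, peak GH and region as categorical, so there is no doubt about how they enter.

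The classes are those used for randomization (sections 4.3 and 6.5): age up to or above 7 years 0 days; peak GH up to 3, above 3 to 7, and above 7 to 10 ng/mL.

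Exact values exist for both. Section 5.1 notes that the birth date is needed for height SDS, and sections 4.1 and 5.1 require numeric GH peaks from two provocation tests. No model in sections 8.6 to 8.6.2 uses continuous age or peak GH, and no reason is given for using classes alone.

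The supplied SAP covers only the long-term extension and contains no ANCOVA. Section 8.5 places the main-study methods in a separate SAP, which is not among the documents.

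**The concern.** Within a class the model treats all children alike: one aged 3 gets the same age term as one aged exactly 7, and a peak of 0.3 ng/mL the same term as 3.0. Any relation between these values and growth within a class stays in the residual.

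The endpoint is raw HV in cm/year, not standardized for age. The protocol's own eligibility rule (section 4.1, criterion 5) judges pre-treatment HV against percentiles for chronological age, so it treats HV as age-dependent. Baseline height SDS is itself age-standardized and cannot be relied on to recover age differences within a class.

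Non-inferiority turns on one lower confidence bound. The design assumes a true deficit of 0.8 cm/year against a margin of 1.8, at 80% power, which leaves little reserve.

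**Working it through.** **Inputs from the protocol** (section 8.1; synopsis, Sample Size Calculation):
- alpha 0.05, two-sided, so 0.025 for the lower bound;
- spread of the endpoint: "Between-patient SD of annual growth rate is 2.5 cm/year in all treatment groups";
- margin −1.8 and assumed true difference −0.8, both in cm/year;
- resulting size: "100 patients per group will provide 80 % power for the non-inferiority test";
- randomized number: 110 in each arm, 220 in all, which covers a loss of about 10%.

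**The plan's own figure.** Distance from the assumed difference to the margin: 1.8 − 0.8 = 1.0 cm/year.
- n per arm = 2 × [2.5 × (1.960 + 0.842) / 1.0]² = 98.1, so 99, against 100 stated.
- At 100 per arm, SE = 2.5 × √(2/100) = 0.354 and power = Φ(1.0/0.354 − 1.960) = 80.7%.
- Dropout: 99 / 0.90 = 110 per arm.

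The stated size reproduces with no covariate adjustment.

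**Share of explained variance that classes keep** (between-class variance over total variance). The covariate distributions are assumptions; the documents do not give them.
- Age even over 3 to 11.5 years, cut at 7: class proportions 4/8.5 = 0.471 and 0.529, class means 4.25 years apart. Share = 0.471 × 0.529 × 4.25² / (8.5²/12) = 0.747. A bell-shaped age distribution gives about 0.67.
- Peak GH cut at 3 and 7: 0.75 to 0.82 on the log scale; about 0.88 on the linear scale with even spread (0.81 if bell-shaped).

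**Effect on residual variance.** Let R² be the share of HV variance that each factor explains. It is not in the documents; the assumed range is 0 to 0.10 each. Overlap with height SDS, gender and region is ignored. As a fraction of total variance:
- classes only: 1 − 0.747·R² − k·R², where k is the share kept for peak GH;
- classes plus exact values: 1 − 2·R².

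Patients gained = 220 × (variance with classes / variance with exact values − 1).

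| R² each | k | Classes | Exact added | Ratio | Patients of 220 |
|---|---|---|---|---|---|
| 0 | any | 1.000 | 1.000 | 1.000 | 0 |
| 0.05 | 0.75 | 0.925 | 0.900 | 0.973 | 6.1 |
| 0.10 | 0.75 | 0.850 | 0.800 | 0.941 | 13.8 |
| 0.10 | 0.82 | 0.843 | 0.800 | 0.949 | 11.9 |
| 0.10 | 0.88 | 0.837 | 0.800 | 0.956 | 10.3 |

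**Exact age alone.** With R² = 0.10 for age and nothing for peak GH: 0.900 / 0.9253 = 0.973, a cut of 2.7%, or about 6 of 220 patients. If peak GH classes also explain variance (R² = 0.10, k = 0.75), the cut is 1 − 0.825/0.850 = 3.0%. With bell-shaped ages and nothing for peak GH it is 1 − 0.900/0.933 = 3.5%.

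**Power at 100 per arm, R² = 0.10 each, k = 0.75.** The documents do not say whether 2.5 is an unadjusted or a residual SD.
- If 2.5 is the residual SD under the class model: SD becomes 2.5 × √0.941 = 2.425, SE 0.343, and power goes from 80.7% to about 83.0%. With exact age alone it is 81.9%.
- If 2.5 is the unadjusted SD: the class model already has SE = 2.5 × √(0.850 × 0.02) = 0.326 and power 86.6%. Exact values give SE 0.316 and 88.5%, a gain of 1.9 points. With k = 0.88 and 74% kept for age, the change is 87.1% to 88.5%.

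**Simulation of the full model** (200 patients, 3,000 runs; gender, region, height SDS and classes in the model, 2.5 as the unadjusted SD, linear effects). At R² = 0.10 each, adding both exact values to the classes moved the SE from 0.3286 to 0.3228 and power from 85.3% to 86.5%. The variance ratio is (0.3228/0.3286)² = 0.965. At R² = 0 the SE rose from 0.3590 to 0.3609, about 0.5%, which is the price of two unused degrees of freedom. With log-shaped true effects at R² = 0.10 each, linear terms added to the classes still helped (0.3315 to 0.3259).

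**The case against.** The strongest reply is that nothing here is wrong. A pre-specified ANCOVA that carries every stratification factor, gender and baseline height SDS matches the randomization and is unbiased. Lost precision widens the interval and makes non-inferiority harder to show. All of this stands. A reader might infer that the classes bias the comparison, could yield a false claim of non-inferiority, or leave the trial short of 80% power. The documents support none of these: the stated sample size reproduces without any adjustment.

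The second reply is that the gain rests on figures the documents lack. That also stands. A reader might infer from the choice of stratification factors that both are known to be strong predictors, but sections 4.3 and 6.5 give no reason for choosing them. Gains larger than those shown need larger R² values. If neither factor predicts HV, there is no gain and the SE rises very slightly.

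The third reply concerns peak GH and carries weight. Peaks come from two different tests out of five agents, from local or central laboratories, and partly from historical results. The documents do not say which peak sets the stratum. Classes need that definition too, but they are less sensitive to assay differences within a class and assume no functional form. Assay noise would reduce the gain. This weakens the case for continuous peak GH and does not touch exact age.

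Finally, the main-study SAP is not available, so further adjusted analyses there cannot be ruled out. The point rests on the protocol text.

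**Conclusion.** The point holds as one of efficiency. The primary model uses class membership alone for two baseline variables whose exact values are on record, and so gives up some precision in the deciding interval.

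The size is modest and depends on the assumed 0 to 10% of HV variance per factor and on the assumed covariate distributions: at most about 6% of residual variance for both values together and about 3% for age alone. The power gain is about 2 points at most under either reading of the SD. The planned analysis would remain acceptable unchanged. The case for changing it is that exact age is known without error and its term is almost free. The case for peak GH is weaker: its calculated gain equals that of age only when its classes keep 75%, and is smaller at 82 to 88% or with assay noise.

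**What to change.** In protocol section 8.6, the synopsis and the main-study SAP (not the supplied extension SAP), keep the stratification classes and add baseline chronological age in years as a continuous covariate. Make the same change in the matching secondary models of section 8.6.1. Fix it before database lock and, because the trial is open-label, before anyone sees outcomes by arm.

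Optionally add continuous peak GH, on the log scale if preferred. It should be the same peak that defines the stratum, so that peak must be stated, and a rule is needed for values below detection.

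Cost: one degree of freedom for age, two with peak GH, out of about 190; one sentence in each document, plus the peak GH definitions if that option is taken. No extra patients, visits or data.

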#### 8.6.1 Secondary Endpoint Analyses

A similar ANCOVA model as used for the primary endpoint will be used to analyze:

- annualized HV at 6 months;
- change in Ht SDS at 6 months;
- change in Ht SDS at 12 months.

Least square mean estimates for the 2 treatments and the 95 % CI of the difference between the treatments will be presented.

Descriptive statistics will also be reported for each of these endpoints.

Descriptive statistics (including univariate 95 % CI) will be reported for BM observed and change from Baseline to 12 months.

Descriptive statistics will be reported for HV and Ht SDS at each visit.

Series plots of mean values +/- SE will be reported for HV and Ht SDS by visit and treatment.

ANCOVA-based statistics will be reported by the categorical terms used in the ANCOVA model: age group, gender, peak GH levels, and region.

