c Historical BA assessment might be accepted if it was done according to the method of Greulich-Pyle no more than 6 months prior to the informed consent form (ICF) signature date. If the patient is eligible, the BA must be repeated at Visit 2 prior to dosing. The Visit 2 scan will be the baseline scan for these patients.

d Local, documented provocation tests that were performed prior to ICF signature, might be accepted by the global study MM according to his/her judgment.

e ITT with serum cortisol response to hypoglycemia is adequate for assessment of adrenal insufficiency and no ACTH stimulation test is required if such results are available. Historical ACTH test is acceptable.

Effective Date: Date of final electronic approval

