REFERENCE THERAPY	
Genotropin® is a daily GH, and is used as the reference therapy in this study. A delivery device (Genotropin® Pen) will be used for daily (evening/bedtime) SC administration of Genotropin® into the region of the upper arms, buttocks, thighs or abdomen (8 locations). Injection sites should be rotated.
 
Starting dose regimen for Genotropin®: 0.034 mg/kg/day (which is equivalent to 0.24 mg/kg/wk divided equally into 7 daily injections).
 
IGF-1 SDS will be monitored throughout the study, and if a patient has an IGF-1 level above +2.0 SDS, they will be requested to return for an unscheduled visit within 4-6 wks after the > +2.0 SDS result, on any day post dose (for Genotropin® treated patients). If their IGF-1 level is still above +2.0 SDS, the most recent dose will be reduced by 15%. They will continue to be monitored for any further dose reduction.

MAIN STUDY ENDPOINTS	
Primary efficacy endpoint:
 
 
• Annual HV in cm/year after 12 months of treatment.
 
 
Secondary efficacy endpoints (Auxology/Clinical):
 
 
• Annualized HV after 6 months of treatment.
 
• Change in Ht SDS at 6 and 12 months, compared to baseline.
 
• Change in bone maturation (BM) at the end of 12 months, compared to Baseline BAa (calculated as BA/CA).
 
 
Secondary endpoints (Biochemical):
 
 
• Absolute IGF-1 and IGF-1 SDS levels on Day 4 (-1) after MOD-4023 dosing across study visits.
 
• IGFBP-3 levels and IGFBP-3 SDS on Day 4 (-1) after MOD-4023 dosing across study visits.
 

SAFETY ENDPOINTS	
 
• Incidence of AEs and serious adverse events (SAEs).
 
• Incidence of anti-MOD-4023 Ab formation (including characterization of the Ab and neutralizing properties).
 
• Local injection site reaction assessment.
 
• Parameters of glucose metabolism: blood fasting glucose, fasting insulin level, HbA1c.
 
• Thyroid (endocrinology) status.
 
• Lipid profile.
 
• All other safety hematology, biochemical parameters and urinalysis.
 
• Physical examination.
 
• Vital signs.
 
• Fundoscopy results- if performed (normal/abnormal).
 
• ECG.
 

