OTHER ENDPOINT(S)	
 
• Proportion of successful single injections out of total number of single injections using the MOD-4023 PEN in USA patients at Wks 1, 2, 3, 4, 5, and
 

a Baseline BA can be taken at either Screening or Visit 2.

Effective Date: Date of final electronic approval

	
6, based on the PAT.
 
 
• Proportion of successful single injections out of total number of single injections using the MOD-4023 PEN in USA patients at Wk 1, based on the OAT.
 
• Comments on the PAT related to successful or unsuccessful injection attempts.
 
• Comments on the OAT related to successful or unsuccessful injection attempts.
 
• Information gained by inspection of returned devices.
 
• QoL core total score measured by the QoLISSY questionnaire at Baseline and month 12 in specific countries.
 

LT-OLE ENDPOINT(S)
	
Safety Endpoints
 
 
• Incidence of AEs and SAEs;
 
• Incidence of anti-MOD-4023 Ab formation (including characterization of the Ab and neutralizing properties);
 
• Local injection site reaction assessment;
 
• Parameters of glucose metabolism: blood fasting glucose, fasting insulin level, HbA1c;
 
• Thyroid (endocrinology) status;
 
• Lipid profile;
 
• All other safety hematology, biochemical parameters and urinalysis;
 
• Physical examination;
 
• Fundoscopy results - if performed (normal/abnormal);
 
• Vital signs;
 
• ECG.
 
 
Auxology/Clinical Endpoints
 
 
• Annual HV in cm/year at each 12-month interval.
 
• Change in height SDS every 12 months (compared to the previous values).
 
• Change in bone maturation (BM) every 12 months, (compared to Week 52 BA (calculated as BA/CA) at completion of LT-OLE year 1 and to previous values from LT-OLE year 2 onwards).
 
 
Biochemical Endpoints
 
 
• IGF-1 and IGF-1 SDS levels on day 4 (-1) after MOD-4023 dosing across study visits.
 
• IGFBP-3 levels and IGFBP-3 SDS on day 4 (-1) after MOD-4023 dosing across study visits.
 

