
Effective Date: Date of final electronic approval

Baseline will be characterized with descriptive statistics (mean, SD, and 95% CI) for each treatment group.

**Primary Efficacy Sensitivity Analysis:** The ANCOVA-based primary efficacy analysis will be repeated using the modified intent-to-treat (mITT) set and the per protocol (PP) set.

The ANCOVA-based primary efficacy analysis will be repeated on the full analysis set using last observation carried forward (LOCF) in place of multiple imputation for the handling of missing data.

OAT and PAT (USA Only)

OAT and PAT results will be summarized by using descriptive statistics.

Proportion and counts of successful single injections out of total number of single injections using the MOD-4023 PEN in USA patients at Wks 1, 2, 3, 4, 5, and 6, based on the PAT will be reported. Similarly, counts and proportion of successful single injections out of total number of single injections using the MOD-4023 PEN in USA patients at Wk 1, based on the OAT will be reported. Details on the criteria constituting a successful single injection based on OAT and PAT, along with statistical methods to be used for descriptive summaries will be included in the SAP.

Comments on the PAT and OAT related to successful or unsuccessful injection attempts

The written comments provided on the PAT and OAT for successful or unsuccessful injection attempts will be listed. Any other written comments will also be listed.

Information gained by inspection of returned devices

Summary of the information gathered by inspecting the returned devices will be reported.

The QoLISSY core total score at Baseline, 12 months and change from Baseline to month 12, for each group will be summarized using descriptive statistics. This will be done for specific countries as listed in the [Appendix L](#).

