#### 8.4.2 Secondary Efficacy Endpoints (Auxology/Clinical)

- Annualized HV after 6 months of treatment;
- Change in Ht SDS at 6 and 12 months, compared to Baseline;
- Change in bone maturation (BM) at the end of 12 months, compared to Screening bone age (BM calculated as BA/CA).

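### Change in bone maturation has no pre-specified between-arm estimate in the protocol, and section 8.4.2 names a different reference scan from the synopsis and section 5.1

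*Protocol*

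**What the plan says.** **Analysis.** Protocol section 8.6.1 lists annualized height velocity at 6 months and change in height SDS at 6 and 12 months for an ANCOVA like the primary one. For these three, "Least square mean estimates for the 2 treatments and the 95 % CI of the difference between the treatments will be presented". For the fourth auxology secondary it says: "Descriptive statistics (including univariate 95 % CI) will be reported for BM observed and change from Baseline to 12 months". The synopsis (Statistical Analysis, Secondary Analyses) gives the same plan. Change in BM compared to "Baseline will be characterized with descriptive statistics (mean, SD, and 95% CI) for each treatment group".

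**Reference scan.** Section 8.4.2 defines the endpoint as "Change in bone maturation (BM) at the end of 12 months, compared to Screening bone age (BM calculated as BA/CA". The synopsis endpoint list has "Change in bone maturation (BM) at the end of 12 months, compared to Baseline BA", with a footnote: "Baseline BA can be taken at either Screening or Visit 2". A child may be admitted on a historical film up to 6 months older than consent. In that case bone age is repeated at Visit 2 before dosing, and the synopsis screening footnote states: "The Visit 2 scan will be the baseline scan for these patients". The footnote in section 5.1 says the same.

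**SAP.** Section 8.5 of the protocol foresees two SAPs, one for the main study and one for the extension. The SAP supplied covers the extension only.

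**The concern.** A confidence interval for the mean change within one arm is not an estimate of the randomized difference. BM is the only one of the four auxology secondaries for which the protocol fixes no such estimate. It gives no reason. For the biochemical markers, by contrast, the synopsis says outright that no between-group comparison is planned.

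The endpoint suits a pre-specified comparison. Appendix D attaches importance to serial bone-age readings in judging growth treatment. Section 5.7.2 blinds the central reader to allocation, which is valuable in an open-label trial. Without a planned estimate, readers may fall back on comparing two intervals by eye, and the choice of covariates is left open until later.

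The second matter is one of definition. For a child admitted on a historical film, the bone age available at screening and the bone age designated as baseline are different readings. Section 8.4.2, read literally, can pick the first; section 8.6.1 and the synopsis point to the second. The older film adds untreated months to a 12-month change. It may also lack a central read, because the section 5.7.2 footnote calls for a Visit 2 scan when the central reader was not used at screening.

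**Working it through.** **1. The plan's own size.** Inputs from section 8.1: SD 2.5 cm/year, margin −1.8, true difference −0.8, two-sided alpha 0.05, power 80%. The distance to the margin is 1.0 cm/year, so n per arm = 2 × (1.96 + 0.842)² × 2.5² / 1.0², which rounds up to 99 against 100 stated. Power at 100 per arm is 80.7%. The figure reproduces, but it concerns height velocity. The documents give no SD or sample size for BM.

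**2. What 100 children per arm would give for BM**, in units of the SD of BM change (equal SDs assumed):
- Half-width of a per-arm 95% CI: 1.96/√100 = 0.196 SD.
- Half-width of a CI for the difference: 1.96 × √(2/100) = 0.277 SD.
- If the SD of change in BA/CA were 0.05, 0.10 or 0.15 (assumed), the difference would be known to within ±0.014, ±0.028 or ±0.042.

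**3. What the planned summaries already allow.** With mean, SD and n per arm, difference = mean(MOD-4023) − mean(Genotropin) and SE = √(s²/n + s²/n), each term from its own arm. If n is not printed, it can be recovered from the SD and the CI width. So an unadjusted difference can be derived. What it lacks is adjustment and pre-specification.

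**4. What baseline adjustment would add.** With equal variances at the two times and baseline correlation r, the SE from ANCOVA relative to raw change is √((1+r)/2). That is 0.87 at r = 0.5 and 0.95 at r = 0.8, so the SE falls by about 13% to 5%. Both correlations are assumed.

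**5. Illustration of an informal comparison by eye.** With equal SEs, two 95% CIs separate only when the means differ by 2 × 0.196 = 0.392 SD. That gap is 0.392/0.277 = 1.41 times what the difference CI needs to exclude zero. Treated as a test, the level is 2 × (1 − Φ(2 × 1.96/√2)) = 2 × (1 − Φ(2.772)) = 0.0056. At a true difference of 0.396 SD, the difference CI has 80% power and non-overlap has 51%.

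**6. How old the historical film could be** (months of 30.44 days):

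| Path from film to first dose | Days | Months |
|---|---|---|
| 6 months before consent + 8-week screening running to dosing | 183 + 56 = 239 | 7.9 |
| Same, with the permitted 4-week extension | 183 + 84 = 267 | 8.8 |
| Same, plus 7 days to randomization and 14 days to Visit 2 | 183 + 84 + 21 = 288 | 9.5 |

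The last row is a stacked worst case. It treats Visit 2 as falling after the screening period, and its 7 days are a recommendation, not a limit.

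**7. Effect on one assumed child.** Take chronological age 7.0 and bone age 5.0 at Visit 2, then 8.0 and 6.2 at Month 12. With the Visit 2 scan, the change is 6.2/8.0 − 5.0/7.0 = +0.061. With a film 0.768 years earlier (182.6 + 84 + 14 days), at chronological age 6.232:

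| Earlier bone-age advance (years per year) | Bone age on film | Change in BM | Shift |
|---|---|---|---|
| 0.5 | 4.616 | +0.034 | −0.026 |
| 0.7 | 4.462 | +0.059 | −0.002 |
| 1.0 | 4.232 | +0.096 | +0.035 |

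The shift can go either way. It applies only to children admitted on historical films.

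**The case against.** Descriptive reporting of BM appears in both the synopsis and the body, so it looks deliberate. Non-inferiority is defined on height velocity alone, and even the ANCOVA-analysed secondaries are labelled supportive. The main-study SAP could add the comparison. On the scan, the synopsis, section 5.1 and the Appendix A footnote on bone age all provide for a Visit 2 scan in historical-film children, and 8.6.1 refers to Baseline, so only one phrase in 8.4.2 is out of line. All of this stands, and it limits the weight of the point. It does not supply the missing estimate or remove the contradiction in the section that defines the endpoint.

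Three stronger inferences are tempting and are not supported:
- **That the trial could not say whether bone age advanced faster on MOD-4023.** The arms are randomized, the reader is blinded to allocation, and the per-arm summaries yield an unadjusted difference.
- **That BM will be judged by overlap of intervals.** No section sets such a rule. The figures in step 5 of the working illustrate informal reading only.
- **That the scan conflict favours one arm.** The historical film precedes randomization, so its use should be balanced in expectation. It can move the mean change in both arms alike and adds mainly noise to the difference.

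A practical objection also stands. The primary ANCOVA relies on multiple imputation, whereas BM has one baseline and one post-baseline reading. A BM model therefore needs its own missing-data statement.

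**Conclusion.** The point holds in a limited form. In the protocol, change in BM is the only auxology secondary without a pre-specified, baseline-adjusted between-arm estimate. The planned sample could support one with a half-width of about 0.277 SD before adjustment, and perhaps 5% to 13% less than raw change with it. These figures assume 100 evaluable children per arm, equal SDs and, for the adjustment gain, a baseline correlation of 0.8 to 0.5. The gap is established for the protocol only, since the main-study SAP was not available.

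Separately, 8.4.2 conflicts with the synopsis and section 5.1 on the reference scan. The consequence is confined to an unstated number of children admitted on historical films. For them the reference could lie roughly 8 to 9.5 months before first dose at the extreme. Neither matter touches the primary conclusion. Both are worth correcting because the corrections are specific and nearly free.

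**What to change.** 1. In section 8.6.1 and the synopsis, add change in BM at 12 months to the supportive ANCOVA list. Use terms for treatment, age group, peak GH, region, gender and baseline BM; the synopsis already prescribes each endpoint's own baseline value for the other three. Report the LS mean difference (MOD-4023 minus Genotropin) with its 95% CI in children with both a baseline and a Month 12 scan, and show the number without both in each arm. Keep the per-arm descriptive statistics.
2. In section 8.4.2, replace the reference to the screening bone age with: *Baseline bone age (the centrally read screening scan, or the Visit 2 scan where a historical film was used for eligibility)*.
3. Carry both into the main-study SAP, or confirm that it already contains them.

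The cost is one more run of an existing model and one changed phrase, with no new data. The small downside is one further supportive analysis, which should carry no multiplicity claim.
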